5.2.1.2 Alanine Transaminase (ALT) Elevations

Abrupt elevation of serum ALT above normal is known to occur spontaneously in patients with CHB during the course of disease, and/or during anti-viral therapy. Transient ALT elevations are not always harmful and may be due to:

- *The underlying disease*
- *Immune clearance of infected hepatocytes*
- *Drug-induced immune-mediated hepatitis*
- *DILI*

Isolated ALT elevations of 2-3 times the baseline value that are self-limited may reflect a desirable treatment-related immunologic response rather than drug toxicity. However, progressive increases or ALT elevations associated with increases in bilirubin without alkaline phosphatase increase should primarily be considered adverse events, i.e. potential DILI.

In the event of ALT elevation > 5x ULN, more frequent monitoring of liver tests should be performed based on medical judgment and other causes of ALT elevations should be investigated. For patients with ALT > 5 × ULN, the following management plan is recommended:

ALT elevations during treatment

- *Isolated ALT elevation with preserved hepatic function (e.g. no significant changes in bilirubin, INR/PT, albumin, and ALP):*
 - *Closely monitor liver function tests (LFTs) (i.e. ALT/AST, bilirubin, albumin, ALP and INR/PT):*
 - *ALT 5 to 10 x ULN: Repeat LFTs every week.*
 - *ALT >10 x ULN: Temporarily interrupt RO7062931 or RO7062931 and PEG-IFN treatment and repeat LFTs twice weekly until ALT level < 5 x ULN. Continue NUC treatment. Consider re-introducing RO7062931 or RO7062931 and PEG-IFN therapy following discussion with medical monitor based on subsequent laboratory results.*
- *ALT flare accompanied by declining liver synthetic and excretory functions (increased bilirubin >2 x ULN, or albumin decline >0.5 g/dL, or INR >1.5) or other signs of hepatic impairment (severe fatigue, nausea, vomiting, right upper quadrant pain):*
 - *RO7062931 or RO7062931 and PEG-IFN will be permanently discontinued, continue NUC treatment.*
 - *Closely monitor liver function tests:*
 - *ALT 5 to 10 x ULN: Repeat LFTs every week.*
 - *ALT >10 x ULN: Repeat LFTs twice weekly until ALT level < 5 x ULN.*
 - *Investigate the participant for potential etiologies of the laboratory changes.*
 - *If alternative reasons/diagnoses cannot explain the laboratory changes, a potential DILI will be considered.*

If ALT elevations are associated with increased HBV DNA levels, virological breakthrough will be suspected (see Section 4.6.1.5.4).

ALT elevations during follow-up

- *Isolated ALT elevation with preserved hepatic function:*
 - *ALT 5 to 10 x ULN: Repeat LFTs every week.*
 - *ALT >10 x ULN: Repeat LFTs twice weekly until ALT level <5 x ULN.*
- *ALT elevation accompanied by declining liver synthetic and excretory functions:*
 - *ALT 5 to 10 x ULN: Repeat LFTs and ALT/AST every week.*
 - *ALT >10 x ULN: Repeat LFTs and ALT/AST twice weekly until ALT level < 5 x ULN.*
 - *Investigate the CHB patient for potential etiologies of the laboratory changes.*
 - *If alternative reasons/diagnoses cannot explain the laboratory changes, a potentially delayed DILI will be suspected and CHB patient will be monitored accordingly.*

In participants who have not discontinued NUC therapy if ALT elevations are associated with increased HBV DNA levels, virological breakthrough will be suspected (see Section 4.6.1.5.4).

The Investigator should aim to exclude development of decompensated liver disease. Patients who develop signs of decompensated liver disease (e.g., ascites, variceal hemorrhage, Child-Pugh Class B or C clinical classification [[Appendix 16](#)]) should discontinue study treatment (Section 4.7.1.1). Patients who develop flares should be monitored more closely with additional unscheduled visits and laboratory assessments.

At the discretion of the Investigator, study treatment can be discontinued.

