Physical Examination ^k	X															X
Vital Signs ⁱ	X		X	X	X	X										X
ECG-12 lead	X															X
Hematology ^d		X		X ^b	X ^b	X ^b	X ^b		X ^b	X ^b		X ^b	X ^b	X ^b	X ^b	
Blood Chemistry ^d		X		X ^b	X ^b	X ^b	X ^b		X ^b	X ^b		X ^b	X ^b	X ^b	X ^b	
Urinalysis ^d		X		X ^b	X ^b	X ^b	X ^b		X ^b	X ^b		X ^b	X ^b	X ^b	X ^b	
TSH	X															
Viral Serology ⁿ	X															
Coagulation ^d		X		X ^b	X ^b	X ^b	X ^b		X ^b	X ^b		X ^b	X ^b	X ^b	X ^b	
Inflammatory Markers ^j			X	X	X	X	X			X						X
Autoantibodies (screening) ^o	X															
Autoantibodies (monitoring) ^m			X ^b			X ^b	X ^b		X ^b	X ^b						X ^b
ADA			X ^b		X ^b	X ^b	X ^b		X ^b	X ^b		X ^b	X ^b	X ^b	X ^b	
Alpha fetoprotein		X														
RBR DNA			X ^b													
Pregnancy Test ^f		X														

Appendix 13
Schedule of Assessments – Part 2c, QW Doses for 48 Weeks, Main Table (cont.)

Period	Discontinuation ^e	Follow Up Visit	Follow Up Visit	Follow Up Visit	Follow Up Visit	Follow Up Visit	Follow Up Visit	Follow Up Visit	Follow Up Visit	Follow Up Visit ^h
Day		week 50	week 52	week 54	week 56	week 58	week 60	week 64	week 68	week 72
		+/-3	+/-3	+/-3	+/-3	+/-3	+/-7	+/-7	+/-7	+/-7
Assessments										
Informed Consent										
Eligibility										
Demography										
Medical History										
Fibroscan ^a										
Physical Examination ^k	X									X
Vital Signs ⁱ	X									X
ECG-12 lead	X									X
Hematology ^d	X		X				X			X
Blood Chemistry ^d	X		X				X			X
Urinalysis ^d	X		X				X			X
TSH										
Viral Serology ⁿ										
Coagulation ^d	X		X				X			X
Inflammatory Markers ^j	X		X							
Autoantibodies (screening) ^o										
Autoantibodies (monitoring) ^m	X									X
ADA	X									X
Alpha fetoprotein										
RBR DNA										
Urine Kidney Biomarkers ^p	X		X							
Pregnancy Test ^f	X									X

Appendix 13
Schedule of Assessments – Part 2c, QW Doses for 48 Weeks, Main Table (cont.)

Period	Screening		Treatment Period													
	D-28 to D-4	Day -7 to -4	Day 1	week 2	week 4	week 8	week 12	week 13	week 18	week 24	week 25	week 30	Week 36	Week 42	week 48	week 49
	notime			+/-3	+/-3	+/-7	+/-7		+/-7	+/-7		+/-7	+/-7	+/-7	+/-7	
Assessments																
FSH ^g	X															
Substance Use		X														
Medications ^c			X													
PK Blood Sample ^q			7	X	2	2	7	X	2	7	X	2	2		7	X
Urine PK Sample ^r			2				2			2			2		2	
NUC PK ^s			2													
HBsAg Quantitative		X	X ^b	X ^b	X ^b	X ^b	X ^b	X ^b	X ^b	X ^b	X ^b	X ^b	X ^b	X ^b	X ^b	X ^b

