HBsAg, HBeAg Qualitative; HBsAg/Anti-HBs Complex; Anti Hbe; AntiHBs		X	X ^b		X ^b	X ^b	X ^b		X ^b	X ^b					X ^b	
Viral Genotypes			X ^b													
HBV DNA, Viral Resistance sequencing		X	X ^b		X ^b	X ^b	X ^b		X ^b	X ^b					X ^b	
HBV RNA, HBcrAg			X ^b		X ^b	X ^b	X ^b		X ^b	X ^b					X ^b	
Clinical Genotyping			X ^l													
Ambulatory Visit	X	X	X	X	X	X	X	X	X	X	X	X	X	X	X	X
Randomisation			X													
Adverse Events	X	X	X	X	X	X	X	X	X	X	X	X	X	X	X	X

Appendix 13
Schedule of Assessments – Part 2c, QW Doses for 48 Weeks, Main Table (cont.)

Period	Discontinuation ^e	Follow Up Visit	Follow Up Visit	Follow Up Visit	Follow Up Visit	Follow Up Visit	Follow Up Visit	Follow Up Visit	Follow Up Visit	Follow Up Visit ^h
Day		week 50	week 52	week 54	week 56	week 58	week 60	week 64	week 68	week 72
		+/-3	+/-3	+/-3	+/-3	+/-3	+/-7	+/-7	+/-7	+/-7
Assessments										
FSH ^g										
Substance Use										
Medications ^c										
PK Blood Sample ^q	X	X	X	X						
Urine PK Sample ^r										
NUC PK ^s										
HBsAg Quantitative	X	X	X	X	X	X	X	X	X	X
HBsAg, HBeAg Qualitative; HBsAg/Anti-HBs Complex; Anti Hbe; AntiHBs	X		X		X	X	X	X	X	X
Viral Genotypes										
HBV DNA, Viral Resistance sequencing	X		X		X	X				X
HBV RNA, HBcrAg	X		X		X	X				X
Clinical Genotyping										
Ambulatory Visit	X	X	X	X	X	X	X	X	X	X
Randomisation										
Adverse Events	X	X	X	X	X	X	X	X	X	X
Previous and Concomitant Treatments	X	X	X	X	X	X	X	X	X	X

Appendix 13

Schedule of Assessments – Part 2c, QW Doses for 48 Weeks, Main Table (cont.)

- a) For those patients who do not have a liver biopsy, Fibroscan® or equivalent test within the past 6 months from Screening.
- b) Pre -dose.
- c) Daily administration of NUC and weekly clinic SC administration of RO7062931 or RO7062931 and PEG-IFN
- d) Blood sample for RO7062931 PK and safety laboratory assessment will also be collected in the event of an SAE.
- e) Discontinuation visit: in case of early termination, a patient should be called for this visit and assessments should be performed as listed.
- f) Blood beta -human chorionic gonadotropin (β -HCG) for pregnancy test at screening, other occasions, at any time a secondary amenorrhea of more than 1 week occurs.
- g) FSH only for females and to confirm post -menopausal status.
- h) If necessary, the patients may be asked to return for additional follow-up visits.
- i) Body weight will be measured at each visit for dosing

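### Minor, cheap improvement: Appendix 13 leaves 8 and 12 weeks between scheduled liver tests in follow-up, although blood is already drawn at visits inside both gaps

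*Combined protocol and SAP*

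**What the plan says.** Appendix 13 lists nine follow-up visits after the last dose at Week 48: Weeks 50, 52, 54, 56, 58, 60, 64, 68 and 72. Windows are ±3 days up to Week 58 and ±7 days from Week 60.

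- The rows "Blood Chemistry ^d" and "Coagulation ^d" are marked at the discontinuation visit and at Weeks 52, 60 and 72, and nowhere else in follow-up. Section 4.6.1.5.1 puts ALT, AST, bilirubin, ALP and albumin in the first panel and PT/INR in the second.
- The row "HBsAg Quantitative" is marked at all nine visits.

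Section 5.2.1.2 has a part on ALT elevations during follow-up. It asks for weekly liver tests at 5 to 10 × ULN and twice-weekly tests above 10 × ULN. Where liver function is declining, it adds: "If alternative reasons/diagnoses cannot explain the laboratory changes, a potentially delayed DILI will be suspected and CHB patient will be monitored accordingly". It also states: "Patients who develop flares should be monitored more closely with additional unscheduled visits and laboratory assessments".

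Three provisions allow for more than the schedule. Footnote h of Appendix 13 says "If necessary, the patients may be asked to return for additional follow-up visits". Section 4.6.1.5.1 lets the investigator take extra samples after an out-of-range result or symptoms. Section 5.3.1 has adverse events asked about at each contact.

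**The concern.** Safety in CHB patients is a primary objective (Section 2.1), and Section 5.2.1.2 expects that liver events may appear after treatment ends. Its follow-up rules, the delayed-DILI assessment and the 24-hour report of ALT or AST at or above 10 × ULN (Section 5.1.3) all start from a laboratory value. The fallback provisions respond to symptoms, an abnormal result or a perceived need. None of them tests a patient who feels well.

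A silent flare that rises and settles between Weeks 52 and 60, or between Weeks 60 and 72, would therefore leave no trace, and a longer one would be found late. What is at stake is how complete and timely the off-treatment liver-safety data are, in the first use of this drug for up to 48 weeks.

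**Working it through.** **1. Scheduled intervals.** The plan states no figure for this, so the starting point is the Appendix 13 rows. Each follow-up row has ten cells that match the ten column headers, so broken table text does not explain the blanks.

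| Interval | Nominal | With windows |
|---|---|---|
| Week 48 to 52 | 28 days | 18–38 |
| Week 52 to 60 | 56 days | 56 ± (3+7) = 46–66 |
| Week 60 to 72 | 84 days | 84 ± (7+7) = 70–98 |

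HBsAg blood is drawn at Weeks 54, 56 and 58 inside the first long gap, and at Weeks 64 and 68 inside the second.

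**2. Like-for-like comparison.** In Part 2a (Appendix 3) the last dose is Day 29. Follow-up chemistry is at Days 36, 43, 57, 85 and 113, so the longest interval is 28 days. Day 113 − Day 29 = 84 days, so Part 2a follow-up covers the first 12 weeks after the last dose. The same period in Appendix 13 is Weeks 48 to 60, where the longest interval is 8 weeks. Part 2a has no visit that corresponds to Weeks 60 to 72.

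**3. How much could be missed.** Flare rate, duration and onset are not in the documents, so these are assumptions shown as ranges. Count weeks from Week 48. Tests now fall at 4, 12 and 24. A flare with onset o (0 to 24) and duration d is seen if a test falls between o and o+d. It is missed if 4 < o < 12−d or 12 < o < 24−d.

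- Uniform onset: missed share = [(8−d) + (12−d)]/24. This gives 12/24, 8/24 and 4/24 for d = 4, 6 and 8.
- Onset falling off with half-life h: missed share = {[2^(−4/h) − 2^(−(12−d)/h)] + [2^(−12/h) − 2^(−(24−d)/h)]} / (1 − 2^(−24/h)). For h = 3, d = 6: [(0.397 − 0.250) + (0.0625 − 0.0156)]/0.996 = 19.4%.

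The 3-week half-life is the one case linked to the protocol. Section 1.3.1 expects liver steady state in about 13 weeks; read as 4 to 5 half-lives, that is about 3 weeks each. That flares follow drug washout is a further assumption.

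| Onset pattern | Missed now (d = 4, 6, 8 weeks) |
|---|---|
| Uniform | 50%, 33%, 17% |
| h = 12 weeks | 46.5%, 31.1%, 13.8% |
| h = 6 weeks | 40.9%, 27.2%, 9.9% |
| h = 3 weeks | 29.3%, 19.4%, 3.8% |

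With tests at 4, 8, 12, 16, 20 and 24, no nominal interval exceeds 4 weeks, so every entry becomes 0. With windows an interval can reach 28 + 14 = 42 days, so a 4-week flare could still sometimes be missed.

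**4. Which visits matter.** Points gained for d = 4 and d = 6:

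| Onset pattern | Week 56 alone | Weeks 64 and 68 |
|---|---|---|
| Uniform | 16.7, 8.3 | 33.3, 25.0 |
| h = 6 weeks | 24.9, 13.9 | 16.1, 13.3 |
| h = 3 weeks | 24.0, 14.7 | 5.3, 4.7 |

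If flares come early, Week 56 is worth more than the two later panels together. If they come late, the reverse holds. The documents do not say which, so both gaps need covering.

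**5. Expected yield (d = 6).** Extra flares recorded = patients × assumed rate × gain.

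- 8 patients: from 8 × 0.05 × 0.194 = 0.08 to 8 × 0.20 × 0.333 = 0.53.
- 30 patients: from 30 × 0.05 × 0.194 = 0.29 to 30 × 0.20 × 0.333 = 2.0.

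**The case against.** The strongest case against is that this is a sampling preference with a small return, and much of that stands. Section 3.1.1.3 stops RO7062931 and PEG-IFN before follow-up, so a result could not change their dosing. Section 5.2.1.2 itself says that transient ALT rises need not be harmful. Uniform onset is the favourable case for the late visits. Section 3.2.3 compares Part 2c safety only qualitatively, with Part 2a/2b placebo data and historical profiles. That placebo follow-up ends 12 weeks after the last dose, so results after Week 60 have no in-trial comparator.

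Some stronger readings are tempting and should be resisted:

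- A reader might infer that the schedule breaches Section 5.2.1.2. It does not: the instruction on closer monitoring concerns patients whose flare is already known.
- A reader might set the 12-week gap against the 4-week spacing in Part 2a. Part 2a has ended by that point, so it supports only the comparison for Weeks 48 to 60. The 6-week maximum during treatment in Appendix 13 is not a like-for-like standard either, because dosing is then under way and a result can change it.
- A reader might infer a need to watch for flares after NUC withdrawal. The words "In participants who have not discontinued NUC therapy" show that some patients may have stopped, but the visible text sets no withdrawal of NUCs.

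What the objection does not remove is the gap itself. Some Appendix 13 footnotes are redacted, but the chemistry and coagulation rows are legible and carry only footnote d, on extra samples at a serious adverse event.

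**Conclusion.** The point holds as a minor, inexpensive improvement. Scheduled liver tests in Appendix 13 follow-up are 8 and then 12 weeks apart, and nothing else in the plan schedules a test for a patient without symptoms. In the first 12 weeks after the last dose, the longest interval is twice that of Part 2a.

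The size is uncertain and probably small: about 0.08 to 0.5 extra recorded flares in a cohort of 8, and 0.3 to 2 in 30. These figures rest on an assumed 5% to 20% rate of silent 6-week flares, nominal visit times and the onset patterns shown. The top of each range needs a 20% rate and uniform onset together. The missed-flare percentages are conditional on a silent flare occurring; they are not estimates of harm, which the documents do not allow. No conclusion is drawn for Appendix 11, whose follow-up columns do not line up in the text available.

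**What to change.** In Appendix 13, add a liver panel (ALT/AST, bilirubin, albumin, ALP) with INR/PT at Weeks 56, 64 and 68. Scheduled liver tests would then fall every 4 weeks from Week 48 to Week 72, with a maximum of 42 days when windows are used in full.

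The cost is 3 panels per patient: 3 × 8 = 24 for a cohort of 8, and 3 × 30 = 90 if expanded to 30. All three are existing blood-draw visits, so an extra tube may be needed but no new visit. Section 5.2.1.2 can stay as it is, and the row "HBV DNA, Viral Resistance sequencing" need not change.

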5.2.1.3 Dose Modifications with PEG-IFN

The intention of Part 2c of the protocol is that patients remain on PEG-IFN until the completion of the allocated treatment period. However, it is possible that some patients will encounter transient or prolonged adverse effects or abnormal laboratory values at some juncture during their participation in the trial leading to potential need for adjustment of the PEG-IFN dosage.

If severe adverse reactions or laboratory abnormalities develop during PEG-IFN therapy, the dose should be modified until the adverse reactions abate. If intolerance persists after dose adjustment, PEG-IFN therapy should be discontinued.

When dose modification of PEG-IFN is required for adverse reactions (clinical and/or laboratory), an initial dose reduction to 135 mcg (adjustment to the corresponding graduation mark for the prefilled syringes) is recommended. Dose reduction to 90 mcg (adjustment to the corresponding graduation mark for the prefilled syringes) may be needed if the adverse reaction persists or recurs. Following improvement of the adverse reaction, re-escalation of the dose may be considered. [Table 1](#) provides guidelines for dose modifications and discontinuation of PEG-IFN for haematological laboratory abnormalities.

Table 1 PEG-IFN Hematological Dose Modifications Guidelines

Laboratory Values	Recommended Dose
ANC < 750 cells/mm ³	Reduce to 135 mcg
ANC < 500 cells/mm ³	Discontinue treatment until ANC values return to more than 1000 cells/mm ³ . Reinstigate at 90 mcg and monitor ANC.
Platelets < 50,000 cells/mm ³	Reduce to 90 mcg
Platelets < 25,000 cells/mm ³	Discontinue treatment

For patients who discontinue PEG-IFN early due to intolerability or if stopping criteria are met, then NUC and RO7062931 should be continued up to 48 weeks. The reasons for discontinuation of PEG-IFN and length of treatment duration will be recorded in the eCRF.

5.3 METHODS AND TIMING FOR CAPTURING AND ASSESSING SAFETY PARAMETERS

The Investigator is responsible for ensuring that all adverse events (see Section 5.1 for definition) are recorded on the Adverse Event eCRF and reported to the Sponsor in accordance with instructions provided in this section and in Sections 5.4-5.6. The Investigator is also responsible for reporting medical device complaints (see Section 5.4.4).

For each adverse event recorded on the Adverse Event eCRF, the Investigator will make an assessment of seriousness (see Section 5.1.2 for seriousness criteria), severity (see Section 5.3.3), and causality (see Section 5.3.4).

5.3.1 Adverse Event Reporting Period

Investigators will seek information on adverse events at each study subject contact. All adverse events, whether reported by the study subject or noted by study personnel, will be recorded in the study subject's medical record. Adverse events will then be reported on the Adverse Event eCRF as follows:

After informed consent has been obtained **but prior to initiation of study drug**, only serious adverse events caused by a protocol-mandated intervention should be reported (e.g., serious adverse events related to invasive procedures such as biopsies). Any other adverse event should not be reported.

After initiation of study drug, all adverse events, regardless of relationship to study drug, will be reported until the last follow-up visit.

After the last follow-up visit, investigators should report any deaths, serious adverse events, or other adverse events of concern that are believed to be related to prior treatment with study drug (see Section 5.6).

5.3.2 Eliciting Adverse Event Information

A consistent methodology of non-directive questioning should be adopted for eliciting adverse event information at all study subject evaluation time-points. Examples of non-directive questions include the following:

“How have you felt since your last clinic visit?”

“Have you had any new or changed health problems since you were last here?”

5.3.3 Assessment of Severity of Adverse Events

Table 2 provides guidance for assessing adverse event severity in the study for Part 1 and Parts 2a and 2b.

Table 2 Adverse Event Severity Grading Scale

Severity	Description
Mild	Discomfort noticed, but no disruption of normal daily activity
Moderate	Discomfort sufficient to reduce or affect normal daily activity
Severe	Incapacitating with inability to work or to perform normal daily activity

Note: Regardless of severity, some events may also meet seriousness criteria. Refer to definition of a serious adverse event (see Section 5.1.2).

For Part 2c, DAIDS toxicity grading scales ([Appendix 18](#)) will be used to assess adverse event severity.

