3.2.3 Rationale for Control Group

[figure not shown]
This phase I study is designed to be adequate and well-controlled. In Part 1, randomization to RO7062931 or placebo will occur in a 4:1 ratio within each of the up to 8 cohorts planned. This is considered sufficient to allow for comparisons of safety and tolerability of active to placebo both within and across cohorts.

In Part 2a, randomization to 3 doses of active or placebo will occur in a 1:1:1:1 ratio. In Part 2b, randomization to active or placebo will be 3:1 (within cohorts). The assessment of dynamic changes of HBsAg in CHB patients, will allow estimating the effect of RO7062931 over placebo. The control patients will also allow for the comparisons of safety of active with placebo.

[figure not shown]
[figure not shown]
It is not considered necessary to include controls within the cohorts of Part 2c. Part 2a and 2b have shown that placebo controls have negligible change in HBsAg levels over time. This information can be leveraged in Part 2c for interpretation of HBsAg dynamics. The safety data from Part 2c will be compared qualitatively against Part 2a and Part 2b placebo data and against well-established historical safety profiles of SoC therapies.

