3.3 OUTCOME MEASURES

3.3.1 Safety Outcome Measures

The safety outcome measures for this study are as follows:

- Incidence and severity of adverse events, including adverse events of special interest (see Section [5.3.1](#)).
- Incidence of laboratory abnormalities based on hematology, blood chemistry, coagulation and urinalysis test results (see Section [4.6.1.5](#)).
- ECGs (see Section [4.6.1.4](#)).

- Vital signs, including blood pressure, heart rate and temperature (see Section 4.6.1.3).

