Appendix 17 Toxicity Table for Grading Injection Reactions

Parameter	Grade 1	Grade 2	Grade 3
Pain	Mild tenderness at injection site	Moderate pain without limitation of usual activities	Severe pain requiring prescription non topical analgesics or limiting usual activities
Erythema average diameter (mm) of skin redness at the site of injection	Present but < 25mm	≥ 25 mm but < 50 mm	≥ 50 mm
Swelling, (same grading as erythema)	Present but < 25mm	≥ 25 mm but < 50 mm	≥ 50 mm
Pruritus	Mild, not requiring any treatment	Requiring topical treatment	Refractory to topical treatment, OR requiring oral or parenteral treatment

Appendix 18

Division of AIDS (DAIDS) Table for Grading the Severity of Adverse Events (for Part 2c of the Study)

Division of AIDS (DAIDS) Table for Grading the Severity of Adult and Pediatric Adverse Events Corrected Version 2.1 July 2017 will be used for assessing adverse event severity (see below table).

For AEs listed in the DAIDS Table, the DAIDS grading table provides an AE severity grading scale ranging from grades 1 to 5 with descriptions for each AE based on the following general guidelines:

- Grade 1 indicates a mild event
- Grade 2 indicates a moderate event
- Grade 3 indicates a severe event
- Grade 4 indicates a potentially life-threatening event
- Grade 5 indicates death (Note: This grade is not specifically listed on each page of the grading table)

For AEs not listed on the DAIDS Grading Table, the Functional Table below should be used to grade the severity of an AE that is not specifically identified in the grading table. In addition, all deaths related to an AE are to be classified as grade 5.

Adverse Event Grading (Severity) Scale (For Part 2c)

PARAMETER	GRADE 1 MILD	GRADE 2 MODERATE	GRADE 3 SEVERE	GRADE 4 POTENTIALLY LIFE- THREATENING
Clinical adverse event NOT identified elsewhere in the grading table	Mild symptoms causing no or minimal interference with usual social & functional activities with intervention not indicated	Moderate symptoms causing greater than minimal interference with usual social & functional activities with intervention indicated	Severe symptoms causing inability to perform usual social & functional activities with intervention or hospitalization indicated	Potentially life-threatening symptoms causing inability to perform basic self-care functions with intervention indicated to prevent permanent impairment, persistent disability, or

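### Adverse event severity is graded on one scale in Parts 2a/2b and another in Part 2c, so severity labels are not like for like in the planned comparison with placebo

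*Combined protocol and SAP*

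**What the plan says.** Section 5.3.3 splits the severity scale by study part. "Table 2 provides guidance for assessing adverse event severity in the study for Part 1 and Parts 2a and 2b". The section then adds: "For Part 2c, DAIDS toxicity grading scales" (set out in Appendix 18) will be used.

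Table 2 has three levels, all defined by discomfort and its effect on daily life. Its moderate level reads: "Discomfort sufficient to reduce or affect normal daily activity". Appendix 18 has five grades. Events listed in the DAIDS table follow event-specific descriptions, and a functional row covers events that are not listed. Grades 1 and 2 are labelled mild and moderate. For the next two levels, "Grade 3 indicates a severe event" and "Grade 4 indicates a potentially life-threatening event".

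Section 3.2.3 explains why Part 2c has no control group and says: "The safety data from Part 2c will be compared qualitatively against Part 2a and Part 2b placebo data". It names historical safety profiles of standard-of-care therapies as a second comparator. Section 3.3.1 lists "Incidence and severity of adverse events, including adverse events of special interest" among the safety outcomes. Sections 6, 6.5 and 6.5.1 provide for descriptive summaries by part, listings and frequency tables. None of them describes a re-grading or a mapping between the scales.

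**The concern.** Part 2c safety has to be read against data from outside Part 2c. The pooled Part 2a/2b placebo patients are the only placebo-treated patients with chronic hepatitis B in the study, and the primary objective in this population is safety compared with placebo (Section 2.1). Severity is one of the things to be compared, and the two sides are graded on different instruments.

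The amendment rationale says that DAIDS was adopted so that hepatitis B data would be consistent and comparable. It does not deal with comparability with the earlier parts of this same study. Section 1.2.2 already reports no severe events and five moderate ones in Parts 2a/2b. A Grade 3 laboratory event in Part 2c would be read against that zero, although Table 2 offers almost no route by which a symptom-free laboratory event could be called severe. At stake is how the severity tables are interpreted. No test or error rate is involved.

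**Working it through.** The plan gives no figure to reproduce. The check sets the two scales side by side and then sizes the groups.

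**1. Same event, two labels.** Inputs: Table 2 (Section 5.3.3), the general guidelines and functional row of Appendix 18, and the ALT cut-offs attributed to DAIDS in Section 4.7.1.1 (Grade 3 above 5 × to below 10 × ULN; Grade 4 from 10 × ULN).

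| Event | Table 2 (Parts 2a/2b) | DAIDS (Part 2c) | Shift from Table 2 to DAIDS |
|---|---|---|---|
| Symptom-free ALT of 6 × ULN, recorded as an adverse event | No level above mild fits, since daily activity is not affected | Grade 3, labelled severe | Up |
| Unlisted symptom, minimal interference, no intervention indicated | May be moderate, since activity is affected | Grade 1 | Down |
| Potentially life-threatening event | Severe is the top level | Grade 4 | Level with no counterpart |
| Unlisted symptom that clearly prevents usual activity | Severe | Grade 3, severe | None |

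The second row rests on the DAIDS Grade 1 wording: "Mild symptoms causing no or minimal interference with usual social & functional activities with intervention not indicated". The first row needs the ALT value to be recorded as an adverse event. Under Section 5.3.5.4 that happens if it brings symptoms, changes study treatment, leads to an intervention or a change in other therapy, or is judged clinically significant.

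**2. Direction.** One row moves up, one moves down, one adds a level and one does not move. The documents do not give the mix of events to expect, so the net shift cannot be signed.

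**3. Size of the groups.** Planned placebo: one Part 2a cohort of 6, plus 2 in each of the three Part 2b cohorts reported in Section 1.2.2, gives 6 + 3 × 2 = 12. Section 1.2.2 reports 27 patients enrolled in each part. Applying the allocation ratios (one quarter placebo in each) gives 27/4 + 27/4 = 13.5, so the actual number is probably 12 to 14. The initial Part 2c cohorts have 8 each.

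Effect of relabelling one patient on a severity proportion:
- placebo: 1/12 = 8.3 percentage points (1/14 = 7.1)
- one Part 2c cohort: 1/8 = 12.5 percentage points

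**4. Size of a re-grading.** Section 1.2.2 reports 82 events in all 54 Part 2a/2b patients at the cut-off. The placebo share is not given. If events were spread evenly over patients (an assumption), it would be 82 × 12/54 = 18 to 82 × 14/54 = 21 events. The ceiling at that cut-off is 82.

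**5. What does not depend on the scale.** Event incidence and seriousness do not. Laboratory values are summarised numerically and flagged against the sponsor's standard and marked ranges without distinction by part (Sections 6.5.2 to 6.5.2.2). Injection-site symptoms are graded on Appendix 17, which is not restricted to any part (Section 5.3.5.1).

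**The case against.** The comparison is qualitative, summaries are reported separately by part, and no cross-part severity table is specified. DAIDS may well serve the second comparator, the historical standard-of-care profiles. The laboratory signals that matter most are already caught by numeric rules: ALT or AST from 10 × ULN is an event of special interest (Section 5.1.3), and ALT with bilirubin or jaundice has its own reporting criteria (Section 5.3.5.6). The placebo patients were dosed for about four weeks under blind. Part 2c is open-label for 24 or 48 weeks, with PEG-IFN in Cohort 10, and a common scale removes none of those differences. All of this stands, and it keeps the point minor. It does not remove it: differences in exposure and co-medication cannot be corrected at analysis, whereas the scale can.

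A reader might infer that laboratory events will be graded systematically higher in Part 2c, so that an excess of severe events is bound to appear. The documents do not support that. Appendix 18 does not reproduce the full DAIDS table, and numeric DAIDS laboratory cut-offs appear only for ALT. Clinical events can move the other way, and many need not move at all. A reader might also take the ALT example for a placebo patient who exists. Section 1.2.2 reports no events of special interest and no significant laboratory changes in Parts 2a/2b at the cut-off, so the example shows the mechanism only.

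**Conclusion.** The point holds in limited form. Following the plan as written places unlike severity labels side by side, and an individual event can change label because of the scale alone. The net direction is unknown. The effect is confined to severity labels in a descriptive comparison of roughly 12 to 14 placebo patients with 8 per initial Part 2c cohort, where one patient is worth about 7 to 12.5 percentage points. Severity: minor.

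This rests on three assumptions: placebo numbers close to the planned allocation; a symptom-free laboratory event being graded mild under Table 2, which is an inference because Table 2 speaks only of discomfort and activity; and the ALT cut-offs in Section 4.7.1.1 matching the DAIDS version used in Part 2c.

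**What to change.** Add a short paragraph to Section 6.5 covering the comparison promised in Section 3.2.3.

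- **Laboratory values.** Derive DAIDS grades by program from the central-laboratory results of both the Part 2a/2b placebo patients and Part 2c, using one definition of ULN and one named DAIDS version. Appendix 18 cites corrected version 2.1 and the reference list cites version 2, so the version needs stating.
- **Clinical events.** Limit the comparison to incidence and seriousness, and state that severity labels are not comparable across parts. Alternatively, re-grade the placebo events on Appendix 18 from existing records and show the recorded Table 2 grade alongside.

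No new data, visits or assessments are needed. The cost is a little programming. If re-grading is chosen, it is a retrospective judgement in a Sponsor-open study, which should be stated in the report. The difference in length of observation (about 16 weeks to Day 113, against 48 or 72 weeks in Part 2c) remains and should be stated beside any worst-grade table.
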